6. STUDY DESIGN

This is a randomized, controlled, open-label, parallel group, multi-center, 5-week pilot study to determine changes in BOE in adult smokers allowed *ad libitum* use of VBM-FG2 relative to adult smokers who are not allowed use of VBM-FG2. The data collected from this study will be used to estimate the variability of differences in the percent change from Baseline to the EOS in urinary total NNAL between Test and Control Groups; these findings will be used to estimate the sample size for a future pivotal study. This study will be conducted in approximately 150 adult

smokers who are considered to be in overall good health. Subjects will be randomized (based on gender, daily cigarette consumption [<20 and 20], and quit attempts [any quit attempts/no quit attempts]) to Test (allowed VBM-FG2 use) or Control (not allowed VBM-FG2 use) product in a 3:2 ratio (90 subjects randomized to Test: 60 subjects randomized to Control) with no more than a 60:40 distribution of either males or females to either group.

Screening	Baseline Period*		Product Use Period ^t			
Visit 1	Visit 2	Visit 3	Visit 4	Visit 5	Visit 6	Visit 7
Day -28 to Day -1	Day 1	Day 8±1	Day 15 ± 1	Day 22 ± 1	Day 29± 1	Day 36 ± 1
Subject evaluated against inclusion and exclusion criteria for study eligibility	Baseline CPD data gathered using recall of previous week and daily IVRS call.		Randomization in a 3:2 ratio (Test:Control) 
 • Test = ad libitum VBM-FG2 • Control = no VBM-FG2 			
Enrollment		Randomization				

*Baseline Period = after the daily IVRS call on Day 1 through the daily IVRS call on Day 8.

^t Product Use Period = after the daily IVRS call on Day 8 through the daily IVRS call on Day 36.

Note: Subjects in both groups are allowed to smoke their regular brand cigarettes during the entire study period

Expected duration of the study, from first subject first visit through last subject last visit is approximately 3 months. Expected duration for each subject is expected to be up to approximately 5 weeks (potentially 9 weeks from Screening to EOS). All subjects will be informed that they are allowed to smoke their own cigarettes or to quit smoking during the study.

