The Product Use Period will begin following the Day 8 \pm 1 IVRS and will continue through Day 36 \pm 1. Subjects in the Test Group will be provided VBM-FG2 for *ad libitum* use. Subjects in both Test and Control Groups will continue daily tobacco use tracking via an IVRS and return to the study site once a week during the 4-week Product Use Period for Visits 4 through 7, Days 15, 22, 29, and 36, respectively. These weekly visits will include collection of urine and blood samples for BOE measurements, dispensing VBM-FG2 supplies (Test Group only, Days 8, 15, 22, 29) and return of VBM-FG2 supplies and collection of empty product packaging (Test Group only, Days 15, 22, 29, 36) as appropriate.

Subjects will be instructed to report all adverse events (AEs) and changes in concomitant medications and if necessary, to return to the study site for further evaluation. During the EOS visit (Day 36 or Early Termination), additional assessments will be performed to confirm the health and well-being of the subject.

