11.4.1 Statistical Analyses of Primary Endpoint

A linear mixed model for repeated measures analysis of variance will be used for the analysis of the primary outcome measure. SAS procedure Proc Mixed will be used for the statistical computing. The null hypothesis is that smokers allowed *ad libitum* use of VBM-FG2 discs (test) will not differ in the primary biomarker (percent change from baseline to EOS in urinary total

NNAL) compared to smokers not allowed use of VBM-FG2 discs (control). The alternative hypothesis is that smokers allowed *ad libitum* use of VBM-FG2 discs will differ in the primary biomarker compared to smokers not allowed use of VBM-FG2 discs. The model will include percent (or absolute) change from baseline to EOS in urinary total NNAL as a response variable, product, visit, and product by visit interaction as fixed effects; and subject as random effect. In the expanded model, several additional factors will be considered. Details about the models are as follows:

Model 1:

Percent (or absolute) change from baseline in total NNAL = study group + visit + study group*visit + subject + random error

Model 2:

Percent (or absolute) change from baseline in total NNAL = study group + visit + study group*visit + subject + CPD + sex + race + body mass index (BMI) + age + random error

where

CPD = fixed covariate representing average number of cigarettes per day for past week from IVRS

study group = fixed effect term (test or control)

sex = fixed effect (male or female)

race = fixed effect (White or Non-White)

BMI = fixed effect covariate

age = fixed effect covariate (continuous)

visit = fixed effect term representing days (ordinal categorical variable)

subject = random subject effect

baseline = Total NNAL measure at Day 8

If the study group*visit interaction term is not statistically significant (P-value > 0.10), then the interaction term will be removed from the model and all comparisons will be done using the overall product means. If the interaction effect is significant (P-value < 0.10), then the comparisons will be conducted for each study visit. Comparisons between products will be done based on 5% level of significance.

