All secondary and exploratory analyses will be conducted on the Per-protocol population only.

A linear regression analysis will be conducted within each group at each timepoint to examine the relationships between levels of all 5 BOEs (dependent variable) with either weekly cigarette counts (Day 1 and 8 from questionnaire) or daily cigarette counts (from IVRS) (independent variable). For total NNAL, the corresponding daily cigarette counts from IVRS will be the average of past 7 days. For other biomarkers, it will be the average of past 2 days. The regression analysis will be conducted on the Per-protocol population.

The proportion of subjects in subgroups will be provided with proportion and sample size based on:

- 1) Cigarette consumption change from Baseline (average of Days 2 to 8 from IVRS) to the last week (no change, <50% reduction, 2::50% reduction , 100% reduction, increase);
- 2) Total NNAL change from Day 8 to the last visit (no change, reduction, increase);
- 3) Total scores of FTCD change from Day 8 to the last visit (increase, no change, decrease)
- 4) Proportion of subjects in subgroups based on Changes from Baseline (Day 1) to EOS (increase, no change, decrease) on the change in Quit Attempts from Day 1 to last visit.
- 5) Proportion of subjects in subgroups based on Changes from Baseline (Day 1) to EOS (yes to no, no to yes, and same) on the change in Quitting Intentions from Day 1 to last visit.

The Mantel-Haenszel Chi-Square Test will be used for (1), (2), (3), and (4); Fisher exact test will be used for (5) to test the frequency differences between the two groups.

Additional statistical analyses:

Wilcoxon signed rank test will be used to test the FTCD score difference between the 2 baseline measures (Visit 2 and 3) for the test group. If there is no statistical significance, the average score will be related to the average amount of VBM-FG2 in the past week via linear regression. Otherwise the FTCD score for Visit 3 will be used.

For the test group only, a simple linear regression model will be used to examine the relationship between COHb and Exhaled CO at each post-baseline visit.

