A stepwise multiple linear regression model will also be used to examine the relationship between each of the 5 BOEs (response variable) and a number of factors including average CPD, average VBM-FG2 use, average use of other products, age, sex, BMI and race at each post-baseline visit for the test group only. The average amount of tobacco product use will be for the past 7 days when total NNAL is the dependent variable and will be for the past two days when other BOE is the dependent variable.

Demographics and Characterization of Tobacco Product Use and Exposure Patterns

Demographic baseline characteristics will be summarized by study group with descriptive statistics. For continuous data, descriptive statistics will include N, mean, median, SD, min, max, coefficient of variation (CV%), and 95% confidence interval (CI). For categorical data, frequency counts and percentages will be presented. Fisher's exact test will be used to test for the differences in categorical variables (sex, race: White versus Non-white, quit attempt, cigarette consumption per day: ≤ 20 and > 20) between the 2 study groups and t test, to test for the differences in continuous variables (age, body weight, height, BMI, Number of times stopped smoking cigarettes for 24 hours or longer in an attempt to quit in past 6 months, Number of years smoked since turning 21 years).

Descriptive statistics will be provided to summarize the use of all tobacco products including cigarettes, VBM-FG2 discs and other products by study group and visit. The mean for each variable will be plotted by study group over time.

For subjects in the test group, a simple linear regression model will be used to examine the relationship between visit average of CPD (from IVRS) and visit average of VBM-FG2 use for all post-baseline visits in the study.

For subjects in the test group, a frequency table will be provided with the responses (definitely would buy and probably would buy) in the VBM-FG2 Potential Purchase Interest Questionnaire as the row variable and their average VBM-FG2 use level (4 discs versus < 4) in the last 2 visits as the column variable. Fisher exact test will be used to test for the association.

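### Read naturally, the regression of cigarette use on VBM-FG2 use pools up to four visits per Test subject with no subject term, so its standard error is probably too small

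*SAP*

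**What the plan says.** Under the heading on demographics and tobacco use patterns in SAP section 11.4.2, a simple linear regression in the Test group relates "visit average of CPD (from IVRS) and visit average of VBM-FG2 use for all post-baseline visits in the study". No subject effect, covariance structure or clustered standard error is given. Section 6 puts the post-baseline visits at "Visits 4 through 7, Days 15, 22, 29, and 36, respectively" and the allocation at "90 subjects randomized to Test: 60 subjects randomized to Control". The analysis set is limited: "All secondary and exploratory analyses will be conducted on the Per-protocol population only".

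Two other Test-group regressions in the same section are worded differently. The carboxyhemoglobin model is "to examine the relationship between COHb and Exhaled CO at each post-baseline visit", and the stepwise biomarker models are fitted "at each post-baseline visit for the test group only". The regressions of biomarkers on cigarette counts are likewise run separately at each timepoint. For repeated change in CPD, section 11.4.2 specifies a linear mixed model with a random subject effect.

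**The concern.** Ordinary least squares treats every record as independent. Four weekly averages from one smoker are not independent if that person's smoking and disc use persist from week to week, which is to be expected of habitual use. When both variables are positively correlated within subject, the pooled fit overstates how much information it has, and the error bar on the slope is too narrow.

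A second, lesser point is that a pooled slope mixes two questions: whether smokers who use more discs smoke more or less than other smokers, and whether a given smoker smokes less in weeks with more disc use. The two can have opposite signs and cancel.

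What is at stake is how the link between cigarette and disc use is described. An association could be reported with more confidence than the data support.

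**Working it through.** The SAP gives no sample size, power or standard error for this regression, so there is no figure to reproduce.

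**Inputs from the SAP**
- Test subjects, n: 90 randomized (section 6).
- Post-baseline visits, m: 4 (section 6).
- Records in a pooled fit: at most 90 × 4 = 360.

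**Assumptions**
- Within-subject correlation (ICC) of each variable: not given, so varied from 0.3 to 0.9, with the same correlation between any two visits.
- Per-protocol size: not known in advance; 72 of 90 used as a sensitivity case (72 × 4 = 288 records).
- Two-sided 5% test: the SAP states this level only for product comparisons.

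**Formulas**
- Design effect D = 1 + (m − 1) × ICC(discs) × ICC(CPD). It is symmetric, so it does not matter which variable is the response.
- True SE ÷ reported SE = √D.
- Effective records = 360 ÷ D.
- Actual type I error = 2 × [1 − Φ(1.96 ÷ √D)].

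For example, at 0.8 for both, D = 1 + 3 × 0.8 × 0.8 = 2.92, √D = 1.71, 1.96 ÷ 1.71 = 1.15, and the type I error is about 0.25.

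| ICC, both variables | D | SE ratio | Effective records | Type I error, formula | Type I error, simulated (n = 90) |
|---|---|---|---|---|---|
| 0.3 | 1.27 | 1.13 | 283 | 0.08 | 0.077 |
| 0.5 | 1.75 | 1.32 | 206 | 0.14 | 0.137 |
| 0.6 | 2.08 | 1.44 | 173 | 0.17 | not run |
| 0.7 | 2.47 | 1.57 | 146 | 0.21 | 0.221 |
| 0.8 | 2.92 | 1.71 | 123 | 0.25 | 0.248 |
| 0.9 | 3.43 | 1.85 | 105 | 0.29 | 0.279 |

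The simulation used 4,000 data sets per setting with a true slope of zero.

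**Sensitivity**
- Unequal correlations of 0.5 (discs) and 0.8 (CPD): D = 1 + 3 × 0.4 = 2.20, SE ratio 1.48, type I error 0.19 (simulated 0.175).
- 72 subjects: the same SE ratios by formula; simulated type I error 0.086 to 0.295 over 0.3 to 0.9.
- No within-subject correlation in disc use: D = 1, so there is no understatement (simulated type I error 0.045).

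**Check of the remedy.** With standard errors clustered by subject, the simulated type I error was 0.050 to 0.061 at 90 subjects and 0.053 to 0.069 at 72.

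**Mixing of slopes.** The pooled slope is approximately ICC(discs) × between-smoker slope + (1 − ICC(discs)) × within-smoker slope. With invented values of 0.7, +0.2 and −0.5 it is 0.7 × 0.2 + 0.3 × (−0.5) = −0.01, so a real within-smoker association would hardly show.

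**The case against.** The strongest reply is that the sentence does not settle whether the fit is pooled. It could mean one regression for every visit, which is how the rest of the section works, or one overall average per subject. Under either reading each model has one record per subject and the independence problem disappears. SAP section 4 leaves detailed output descriptions to a table shell document that is not at hand. This stands as a limit: pooling is the natural reading because the wording departs from its neighbours, but it is not certain.

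It also stands that no test is attached to this regression. The SAP's rule is "Comparisons between products will be done based on 5% level of significance", which concerns the study groups. A reader might infer a definite false-positive rate from the table above; the documents support only a range that depends on assumed correlations and on a test being reported.

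Three further inferences go too far:
- **That the slope is the trial's answer on whether discs replace cigarettes.** It matches no objective in section 5 and no endpoint in section 11.3. The effect of access to discs on smoking is addressed by the randomized comparison of change in CPD, which does have a subject effect.
- **That a within-subject slope would estimate substitution.** Disc use is self-selected, so either slope is observational.
- **That the carboxyhemoglobin and exhaled CO regression shares the fault.** It is fitted at each visit with one record per subject and serves here as a contrast.

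**Conclusion.** The point holds for the natural, pooled reading: up to 360 records from at most 90 subjects, no subject term, and a standard error that is too small whenever both variables are positively correlated within subject. The understatement is a factor of about 1.13 to 1.85 for equal correlations of 0.3 to 0.9, and 1.44 to 1.71 for 0.6 to 0.8. If a 5% test is reported, its type I error would be about 8% to 29%, and 17% to 25% in the narrower range. These figures rest on assumed correlations, constant between visits.

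Under a per-visit reading the fault is only unclear wording. The consequences are limited either way: this is an exploratory description of use patterns, and the primary NNAL comparison and the randomized CPD comparison do not depend on it. It is still worth correcting, because the SAP already uses the right tool for change in CPD.

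**What to change.** State in SAP section 11.4.2 whether the fit is pooled or by visit.

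- **If pooled:** use a linear mixed model with a random subject effect, or keep the linear regression and cluster the standard errors by subject. Optionally, split disc use into each subject's mean and the visit's deviation from it, report both slopes, and label both as observational. Clustering alone corrects the error bar but does not separate the two slopes.
- **If separate fits were meant:** use the same per-visit wording as the neighbouring regressions.

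The cost is a sentence in the SAP and a few lines of code. No data collection or sample size changes.

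### The test of purchase interest against VBM-FG2 use cuts average use at 4 discs; a rank-sum comparison of uncut use with an estimate would be a cheap, low-severity improvement

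*SAP*

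**What the plan says.** SAP section 11.4.2, under Demographics and Characterization of Tobacco Product Use and Exposure Patterns, states for the Test Group that "a frequency table will be provided with the responses (definitely would buy and probably would buy) in the VBM-FG2 Potential Purchase Interest Questionnaire as the" rows, with "their average VBM-FG2 use level (4 discs versus < 4) in the last 2 visits as the column variable". It adds that "Fisher exact test will be used to test for the association". No estimate or interval is named for this comparison, and the section gives no reason for a cut at 4. The cut is read here as 4 or more against fewer than 4, in discs per day. A comparison sign was probably lost when the text was extracted, and that is not held against the plan.

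Elsewhere disc use stays a quantity. Section 6 says that "Subjects in both Test and Control Groups will continue daily tobacco use tracking via an IVRS". Section 11.4.2 plans a regression on the "relationship between visit average of CPD (from IVRS) and visit average of VBM-FG2 use for all post-baseline visits in the study", and also enters average disc use in the FTCD regression and the stepwise biomarker regressions. Appendix 2 lists summary statistics of discs per day.

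**The concern.** Reducing a quantitative average to two classes discards the differences within each class. Fisher's exact test on the resulting table is also conservative at this sample size. The planned test may therefore miss an association that the same data would show uncut, and a p-value alone gives no idea of its size.

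The question has some practical interest. Section 6 lets subjects continue screening only if they answer that they definitely or probably would buy the product. Whether the stronger answer goes with heavier use could be useful to those planning the pivotal study.

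**Working it through.** **No figure to reproduce.** Section 8 gives no power, effect size or distribution for this analysis or for the trial. The only checkable number is the allocation: "3:2 ratio (90 subjects randomized to Test: 60 subjects randomized to Control", and 150 x 3/5 = 90.

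**Inputs from the SAP.**
- At most 90 subjects, since "All secondary and exploratory analyses will be conducted on the Per-protocol population only".
- The cut at 4 and Fisher's exact test (11.4.2).

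**Assumed inputs.**
- Two-sided 5%. Section 11.4.1 says "Comparisons between products will be done based on 5% level of significance", which covers product comparisons only.
- Split of definitely/probably answers: 45/45 or 30/60.
- The distribution of disc use and the effect size, varied below.

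**Step 1: closed-form check, normal data, 45 per group, cut at the median.**
- Difference giving the uncut comparison 80% power: d = (1.960 + 0.842) x sqrt(2/45) = 0.591 SD.
- Shares above the cut: Φ(0.591/2) = 61.6% and 38.4%.
- Power of the uncorrected two-proportion test: Φ[(0.232 x sqrt(45) − 1.960 x sqrt(0.5)) / sqrt(2 x 0.616 x 0.384)] = Φ(0.25) = 60%.
- To regain 80% takes 72 per group, or 80 with continuity correction: 72/45 = 1.6 and 80/45 = 1.8 times as many.
- Simulated (3,000 runs): Fisher 50%, Wilcoxon 77%. With 30% or 20% of subjects at or above the cut, Fisher falls to 48% or 38%, and Wilcoxon stays at 77-78%.
- With no true difference, Fisher's actual size is about 2.5% at 45/45 and 4.0% at 30/60, against a nominal 5%.

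**Step 2: log-normal use, log-SD 0.9, cut at 4, median use 2, 4 or 8 discs (4,000 runs per setting).** The gap is taken from the ends of the two ranges.

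| Split | True ratio of use | Fisher | Wilcoxon | Gap (points) |
|---|---|---|---|---|
| 45/45 | 1.5 | 23-29% | 53-54% | 24-31 |
| 45/45 | 1.8 | 48-60% | 84-85% | 24-37 |
| 30/60 | 1.5 | 26-35% | 49-50% | 14-24 |
| 30/60 | 1.8 | 48-62% | 80-81% | 18-33 |

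- At log-SD 1.3 and a ratio of 1.5: Fisher 14-19%, Wilcoxon 26-30%, a gap of 7 to 16 points.
- If median use is only 1 disc, so that few subjects reach 4, Fisher at 45/45 falls to about 6-16%. Wilcoxon is unaffected by the median, so in that corner the gap can exceed 45 points.

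**Step 3: skewed daily counts (gamma-Poisson, averaged over 14 days, cut at 4, 2,000 runs).** Fisher 22-78%, Wilcoxon 47-93%, with a gap of about 11 to 42 points across the scenarios.

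**Step 4: two clusters.** Subjects are either adopters (median 6 discs) or occasional users (median 0.8), and the purchase answer shifts only the chance of adoption.

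| Adoption, definitely/probably | Fisher v Wilcoxon, 45/45 | Fisher v Wilcoxon, 30/60 |
|---|---|---|
| 50% / 25% | 48% v 52% | 46% v 47% |
| 40% / 15% | 53% v 50% | 56% v 48% |
| 60% / 30% | 62% v 69% | 59% v 62% |

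Here Fisher ranges from 7 points worse to 8 points better. Over a wider set of such patterns it ranged from an 18-point loss to an 11-point gain. The tighter the two clusters, the more the balance tips towards Fisher.

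**The case against.** The strongest reply is that nothing the trial sets out to do depends on this table. Purchase interest against disc use is not among the objectives (sections 5.2 and 5.3) or the endpoints (11.3). Section 8 describes a pilot meant to measure the variability of the primary outcome. Low power in one exploratory table of such a study is not in itself an error. This stands, and it sets the severity.

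Three stronger readings are tempting, and the documents do not support them.
- **That the cut must waste much of the power.** Under a smooth shift it does; under two clusters around 4 discs it may waste none. The SAP gives no distribution to choose between these.
- **That the rank-sum test would make a null result informative.** At a 1.5-fold difference and log-SD 0.9, Wilcoxon itself has only about 49-54% power, and about 26-30% at log-SD 1.3. The estimate and interval help more here than the p-value does.
- **That the plan discards the disc counts or chose 4 arbitrarily.** The counts are summarised, plotted and used in regressions. A classification into heavier and lighter users is a legitimate descriptive question, and a reason for the cut may stand in the protocol or the TFL shells, which are not at hand.

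What survives is narrow. The one planned test of purchase interest against use relies on the cut variable alone, with no estimate, when the uncut average is already to hand.

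**Conclusion.** The point holds as a low-severity, inexpensive improvement. Under a smooth difference in use (log-normal, log-SD 0.9 to 1.3, at most 90 Test subjects, two-sided 5%), the planned test gives up roughly 10 to 45 points of power against a rank-sum test, and it has very little power if few subjects reach 4 discs. Under sharply bimodal use around the cut, the loss is small or absent. The split of purchase answers, the distribution of use and the effect sizes are all assumptions. No conclusion on total NNAL or on any listed endpoint is affected.

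**What to change.** In SAP section 11.4.2, make the tested comparison average discs per day over the last 2 visits, definitely against probably would buy, by Wilcoxon rank-sum test, with a Hodges-Lehmann difference and 95% CI. Keep the 4-disc frequency table as description, without a test. If the cut at 4 has a meaning, state it there.

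The cost is one SAP sentence and the matching output, with no new data or visits. The downside is a possible loss of some power, probably small, if use turns out sharply bimodal around 4 discs; the retained table would still show that pattern.
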